8.5.2. Secondary Analyses

The secondary endpoint of proportion of participants with treatment emergent AEs will be compared between each of the RDV groups and standard of care group in Part A using a Fisher's Exact test. The point estimates of the treatment differences and the associated 95% confidence intervals will be provided. Other endpoints of interest related to proportion of participants will be compared between treatment groups in Part A using a chi-square test or Fisher's Exact test. Efficacy endpoints that are measured as time to first event will be compared between treatment groups using a competing risk model (with death as the competing risk) and continuous endpoints will be compared between treatment groups using a Wilcoxon rank sum test or analysis of variance model.

The 7-point ordinal scale of clinical status and other efficacy endpoint of interest will be summarized descriptively for Part B.

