2. OBJECTIVES

The purpose of this study is to provide RDV to participants with moderate COVID-19.

The primary objective of this study is as follows:

- To evaluate the efficacy of 2 RDV regimens compared to standard of care (SOC), with respect to clinical status assessed by a 7-point ordinal scale on Day 11

The secondary objective of this study is as follows:

- To evaluate the safety and tolerability of RDV compared to SOC

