7. ADVERSE EVENTS AND TOXICITY MANAGEMENT

7.1. Definitions of Adverse Events and Serious Adverse Events

7.1.1. Adverse Events

An AE is any untoward medical occurrence in a clinical study subject administered an investigational product, which does not necessarily have a causal relationship with the treatment. An AE can therefore be any unfavorable and/or unintended sign, symptom, or disease temporally associated with the use of an investigational product, whether or not considered related to the investigational product. AEs may also include pretreatment or posttreatment complications that occur as a result of protocol specified procedures or special situations (Section 7.6).

An AE does not include the following:

- Medical or surgical procedures such as surgery, endoscopy, tooth extraction, and transfusion. The condition that led to the procedure may be an AE and must be reported.
- Preexisting diseases, conditions, or laboratory abnormalities present or detected before the screening visit that do not worsen
- Situations where an untoward medical occurrence has not occurred (eg, hospitalization for elective surgery, social and/or convenience admissions)
- Overdose without clinical sequelae (Section 7.6.1)
- Any medical condition or clinically significant laboratory abnormality with an onset date before the consent form is signed and not related to a protocol-associated procedure is not an AE. It is considered to be preexisting and should be documented as medical history.
- Preexisting events or conditions that increase in severity or change in nature after the consent form is signed or as a consequence of participation in the clinical study will be considered AEs

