7.2.1. Assessment of Causality for Study Drugs and Procedures

The investigator or qualified subinvestigator is responsible for assessing the relationship to study drug using clinical judgment and the following considerations:

- **No:** Evidence exists that the AE has an etiology other than the study drug. For SAEs, an alternative causality must be provided (eg, preexisting condition, underlying disease, intercurrent illness, or concomitant medication).
- **Yes:** There is reasonable possibility that the AE may have been caused by the study drug.

It should be emphasized that ineffective treatment should not be considered as causally related in the context of AE reporting.

The relationship to study procedures (eg, invasive procedures such as venipuncture or biopsy) should be assessed using the following considerations:

- **No:** Evidence exists that the AE has an etiology other than the study procedure.
- **Yes:** The AE occurred as a result of protocol procedures (eg, venipuncture).

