7.3.2. Adverse Events

Following initiation of study medication, collect all AEs, regardless of cause or relationship, throughout the duration of the study, including the protocol-required post treatment follow-up period must be reported on the eCRFs as instructed.

All AEs and clinically significant laboratory abnormalities will be followed until resolution or stability of the abnormality has been demonstrated if possible. Gilead may request that certain AEs be followed beyond the protocol-defined follow-up period.

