8.1.3. Secondary Endpoints

The secondary endpoint of this study is:

- The proportion of participants with treatment emergent adverse events

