8.6.2. Adverse Events

Clinical and laboratory AEs will be coded using the Medical Dictionary for Regulatory Activities (MedDRA). System Organ Class (SOC), High-Level Group Term (HLGT), High-Level Term (HLT), Preferred Term (PT), and Lower-Level Term (LLT) will be attached to the clinical database.

Events will be summarized on the basis of the date of onset for the event. A treatment-emergent AE will be defined as any AE that begins on or after the randomization date up to the date of last dose of study drug plus 30 days, or up to Day 28, whichever is the later date.

Summaries (number and percentage of participants) of treatment-emergent adverse events (TEAEs) (by SOC, and PT) will be provided by treatment group.

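### The only secondary endpoint, any treatment-emergent AE, also counts worsening COVID-19, so the planned efficacy would lower the RDV rate and could partly mask a toxic excess

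*Protocol*

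**What the plan says.** The secondary objective (Protocol 2) is "To evaluate the safety and tolerability of RDV compared to SOC". One endpoint serves it (Protocol 8.1.3): "The proportion of participants with treatment emergent adverse events". Protocol 8.5.2 sets the test: "The secondary endpoint of proportion of participants with treatment emergent AEs will be compared between each of the RDV groups" and the SOC group in Part A, using Fisher's exact test with a difference and 95% confidence interval.

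Three other sections decide what enters the proportion:

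- Protocol 7.1.1 leaves out preexisting disease only when it does not worsen. It classes as AEs "Preexisting events or conditions that increase in severity or change in nature after the consent form is signed". That sentence stands as a bullet in a list of things that are not AEs, but its own wording is clear and agrees with the earlier bullet.
- Protocol 7.3.2 tells sites to "collect all AEs, regardless of cause or relationship, throughout the duration of the study".
- Protocol 8.6.2 sets the start of the window: "A treatment-emergent AE will be defined as any AE that begins on or after the randomization date". It ends at the later of last dose plus 30 days or Day 28.

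Protocol 7.2.1 adds that "ineffective treatment should not be considered as causally related in the context of AE reporting". This governs attribution to study drug. The endpoint is not restricted to related events, so the sentence removes nothing from the count.

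**The concern.** Eligibility requires an oxygen saturation above 94% on room air at screening (Protocol 4.2). A participant who later needs oxygen or ventilation, or who dies, has generally moved to a worse category of the primary scale and also had a countable AE. The one tested safety contrast therefore contains part of the efficacy outcome.

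The stake is interpretation. If RDV has the benefit the sample size assumes, fewer RDV participants have a worsening event. The any-AE difference shifts in favour of RDV even when the drug adds no safety advantage, and it offsets some of any real toxicity. A difference near zero could then mean no toxicity and no benefit, or some of each. The test cannot tell these apart.

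**Working it through.** **Inputs.** From Protocol 8.9: SOC on Day 11 in categories 1 to 7 = 0.5, 2.5, 7, 8, 15, 27 and 40%; odds ratio 1.8; 200 per group; two-sided 0.05. Assumed, because the documents do not give them: the rate r of AEs other than COVID-19 worsening, independence of the two kinds of event, and two-sided 0.05 for the Fisher test.

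**The plan's own figure.** Shifting the SOC distribution by an odds ratio of 1.8 and averaging the two arms gives 1 − Σp³ = 0.8752. With θ² = (ln 1.8)² = 0.3455 and 400 participants in the two groups, √(400 × 0.3455 × 0.8752 / 12) = 3.175. Then 3.175 − 1.960 = 1.215, which is a power of 88.8%. The stated figure of more than 85% is reproduced, so the distribution and shift are the plan's own.

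**Worsening by arm on Day 11.**

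- Categories 1 to 4: SOC 0.5 + 2.5 + 7 + 8 = 18.0%. RDV odds = (0.18/0.82)/1.8 = 0.1220, or 10.9%. Fall: 7.1 points.
- Categories 1 to 3: SOC 10.0%. RDV odds = (0.10/0.90)/1.8 = 0.0617, or 5.8%. Fall: 4.2 points.

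**Any-AE rate with no toxicity.** With worsening rate w, the rate is 1 − (1 − w)(1 − r). The fall on RDV is the fall in w multiplied by (1 − r).

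| Other-AE rate r | SOC, cat. 1–4 | RDV, cat. 1–4 | Fall, cat. 1–4 | Fall, cat. 1–3 |
|---|---|---|---|---|
| 0% | 18.0% | 10.9% | 7.1 | 4.2 |
| 20% | 34.4% | 28.7% | 5.7 | 3.3 |
| 40% | 50.8% | 46.5% | 4.3 | 2.5 |
| 60% | 67.2% | 64.3% | 2.9 | 1.7 |
| 80% | 83.6% | 82.2% | 1.4 | 0.8 |

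An independent toxic event in a fraction t of RDV participants cancels the fall when (1 − w_RDV)(1 − t) = 1 − w_SOC. For categories 1 to 4, t = 1 − 0.82/0.8913 = 8.0%. For categories 1 to 3, t = 1 − 0.90/0.9419 = 4.4%. Both hold at any r.

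**Chance of detecting toxicity.** Suppose RDV raises the other-AE rate from 30% to 40%. Power of Fisher's exact test by full enumeration at 200 per arm:

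- All-cause, no efficacy: 1 − 0.82 × 0.70 = 42.6% against 1 − 0.82 × 0.60 = 50.8%; power 34%.
- All-cause, odds ratio 1.8, categories 1 to 4: 42.6% against 1 − 0.8913 × 0.60 = 46.5%; power 10%.
- All-cause, odds ratio 1.8, categories 1 to 3: 1 − 0.90 × 0.70 = 37.0% against 1 − 0.9419 × 0.60 = 43.5%; power 23%.
- Progression events excluded: 30% against 40%; power 52%.

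For a smaller excess, 40% against 45% with progression excluded, power is about 15%. The half-width of the 95% interval is 1.96 × √(0.40 × 0.60/200 + 0.45 × 0.55/200) = 9.7 points.

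**The case against.** The strongest reply is that toxicity is not judged on this row alone. Protocol 8.6.2 tabulates AEs by system organ class and preferred term for each group, so respiratory progression can be seen apart from other events. Protocol 8.6.3 gives graded laboratory abnormalities by group, covering the transaminase elevations named as the specific risk in Protocol 1.5. The monitoring committee reviews safety regularly (8.2.1.1). This stands, and it limits the harm. These are descriptive outputs, however; the tested contrast remains the mixed one.

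The size is also uncertain:

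- Room air is required at screening, up to 2 days before randomization (Protocol 6.2.1), and only mechanical ventilation is excluded (4.3). Protocol 3.1 defines endpoints for baseline scores of 2 to 4, and SAP 3.4.1 plans a low-flow-oxygen baseline subgroup in Part B. Category 4 on Day 11 is therefore not all new worsening, hence the second column of falls.
- Participants who deteriorate may be more likely to have other AEs, which would shrink the fall. Temporary worsening that has resolved by Day 11 would enlarge it.
- The trial is open-label (5.1.2), so reporting may be fuller on RDV. The AE window can run past Day 28 on RDV only: Day 5 or Day 10 plus 30 days, against Day 28 for SOC. Protocol 8.6 summarises safety data through the Day 28 visit, so this effect is probably small.

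The supplied SAP covers Part B only. SAP 2.1.2 refers to a separate Part A SAP, and AE recording also follows eCRF guidelines; neither was available. Progression terms may be handled there.

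A reader might infer that the plan will hide toxicity about as large as the benefit, or will read no difference in AEs as no added toxicity. The documents support neither. Near-complete cancellation needs particular values of an AE rate they do not give, the net direction after the offsets is not established, and no section states such a rule.

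**Conclusion.** The point holds as a partial masking of one tested comparison. The tested secondary endpoint counts disease worsening, and the planned benefit would reduce it. The reduction lies between 7.1 and 1.4 points if categories 1 to 4 are all new worsening, and between 4.2 and 0.8 points if only categories 1 to 3 are, for other-AE rates from 0% to 80%. This rests on the odds ratio of 1.8 being true, Day 11 status standing in for worsening events, sites recording progression as AEs, and independence from other AEs.

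It does not show that the safety assessment as a whole would miss toxicity, or that the any-AE comparison must favour RDV on balance. It justifies an inexpensive supplementary analysis. The all-cause endpoint is conventional and should stay.

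**What to change.** In Protocol 8.5.2, keep the all-cause comparison and add a supplementary one with the same Fisher test, difference and 95% confidence interval. It would compare treatment-emergent AEs after excluding a list of preferred terms for COVID-19 and its respiratory progression. Draw the list up without reference to data by arm. Keep in the count any event the investigator judged related to study drug, so that a drug-related respiratory event is not lost; this can add events only on RDV, which is the cautious direction. Interpret tolerability from both comparisons together with the preferred-term and laboratory tables.

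SAP 2.1.2 and 2.1.3 report the Part A analyses as already performed. If so, the list cannot be called prespecified and the comparison should be labelled supplementary.

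The cost is one term list and one table from AE data already collected. Protocol 8.8 plans no adjustment beyond the primary endpoint, so no alpha is affected. The downsides are some judgement in the list and limited precision: with 200 per arm, the chance of detecting 45% against 40% stays at about 15%.

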8.6. Safety Analysis

All safety data collected on or after the randomization date through the Day 28 follow-up visit will be summarized by treatment group (according to the study drug received). Data for the pretreatment period will be included in data listings. Part A and Part B will be summarized separately.

8.6.1. Extent of Exposure

A participant's extent of exposure to study drug data will be generated from the study drug administration data. Exposure data will be summarized by treatment group for the RDV groups.

8.6.2. Adverse Events

Clinical and laboratory AEs will be coded using the Medical Dictionary for Regulatory Activities (MedDRA). System Organ Class (SOC), High-Level Group Term (HLGT), High-Level Term (HLT), Preferred Term (PT), and Lower-Level Term (LLT) will be attached to the clinical database.

Events will be summarized on the basis of the date of onset for the event. A treatment-emergent AE will be defined as any AE that begins on or after the randomization date up to the date of last dose of study drug plus 30 days, or up to Day 28, whichever is the later date.

Summaries (number and percentage of participants) of treatment-emergent adverse events (TEAEs) (by SOC, and PT) will be provided by treatment group.

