6.5. Day 28 Follow up Assessment (\pm 5 Days)

The following evaluations are to be completed if this visit is conducted in person. For participants who have been discharged from hospital, the final evaluation can be made by phone. Only AE and concomitant medication and ordinal scale (if discharged on or after Day 14) review are to be completed if visit is conducted by phone.

- Physical examination and vital signs (heart rate, temperature, blood pressure)
- Documentation of respiratory status:

Respiratory rate

— Oxygen supplementation: room air, low flow O₂ (L/min and %), high flow O₂ (L/min and %), CPAP/BIPAP (FiO₂ or %), mechanical ventilation (FiO₂ or %), ECMO

Oxygenation: SpO₂ or PaO₂

Radiographic findings (if available)

- Review AEs and document concomitant medications
- Review the Ordinal Scale (Section 6.9). If subject was not discharged by Day 14, any change in category and the date of any change in category from Day 14 to discharge (or Day 28) should be recorded

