6.10. Post-treatment Assessments

No assessments are required after Day 28.

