7.3.1. Requirements for Collection Prior to Study Drug Initiation

After informed consent, but prior to initiation of study medication, the following types of events must be reported on the applicable eCRFs: all SAEs and AEs related to protocol-mandated procedures.

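### Part A adverse event comparison: read by the calendar, the treatment-emergent window ends up to 5 usable days later for remdesivir than for standard of care. The effect is small and a common end date removes it.

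*Protocol*

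**What the plan says.** **Endpoint and test.** Protocol 8.1.3 names one secondary endpoint: "The proportion of participants with treatment emergent adverse events". Protocol 8.5.2 says how it is tested in Part A: "The secondary endpoint of proportion of participants with treatment emergent AEs will be compared between each of the RDV groups and standard of care group", by Fisher's exact test.

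**Counting window.** Protocol 8.6.2 starts the window at randomization in every arm and runs it "up to the date of last dose of study drug plus 30 days, or up to Day 28, whichever is the later date".

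**Limits on what can be counted.** Protocol 8.6 sets the scope of the safety tables: "All safety data collected on or after the randomization date through the Day 28 follow-up visit will be summarized by treatment group". Section 6.5 and Appendix 2 allow that visit 5 days either side of Day 28. Section 6.10 adds: "No assessments are required after Day 28".

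**Dosing.** Under Protocol 3.4, Group 1 is scheduled for 5 days of RDV, Group 2 for 10 days and Group 3 for none. RDV stops at discharge, so a last dose can fall as early as Day 1.

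**Analysis plan.** The supplied SAP covers Part B only, where everyone in the primary analysis set has been dosed (SAP 3.1.2). SAP 2.1.2 refers to a separate Part A Primary Analysis SAP, which was not supplied.

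**The concern.** The end of the window is tied to a dosing date that one of the compared arms does not have. An event with onset on Day 31, recorded at a visit on Day 33, counts for an RDV participant and not for an SOC participant. The secondary objective (Protocol 2) is safety and tolerability compared with SOC, so a counting rule that differs by arm enters the test of that objective directly. It can only raise the RDV proportion relative to SOC. It would not hide harm from RDV, but it could make a difference appear, or look larger, for a reason unrelated to the drug.

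**Working it through.** The plan states no event rate, power or sample size for this comparison, so there is no plan figure to reproduce. The stated power of more than 85% (Protocol 8.9) concerns the primary endpoint.

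**1. Window ends (8.6.2, calendar reading)**

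- RDV, last dose Day 1: 1 + 30 = Day 31
- RDV, last dose Day 5: 5 + 30 = Day 35
- RDV, last dose Day 10: 10 + 30 = Day 40
- SOC: Day 28

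On paper, a full course gives 7 or 12 extra days.

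**2. Usable excess**

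With the limit in 8.6 and a visit on Day 23 to Day 33 (6.5):

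excess = max(0, min(last dose + 30, visit day) - 28)

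- Visit on Days 23-28: 0, which is 6 of the 11 possible days.
- Visit on Day 33: 5 days if the last dose was on Day 3 or later, 4 if on Day 2, 3 if on Day 1.
- Visits spread evenly over the 11 days (assumed), last dose on Day 3 or later: (1 + 2 + 3 + 4 + 5)/11 = 15/11 = 1.36 days on average. A last dose on Day 2 gives 14/11 = 1.27, and on Day 1 gives 12/11 = 1.09.

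**3. Effect on the proportion**

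Assumptions: the true 28-day risk p is 20-60% in both arms, and the hazard after Day 28 is f times the earlier hazard, with f from 0.25 to 1.

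h = -ln(1 - p)/28; RDV risk = 1 - (1 - p) exp(-h f × 1.36)

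Example with p = 40%, f = 1: h = 0.01824, and RDV risk = 1 - 0.6 × exp(-0.01824 × 1.36) = 41.47%. That is 1.47 points, or about 2.9 participants per 200.

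**4. Effect on the test**

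The last three columns give the exact probability, at 200 versus 200 with no true difference, that two-sided Fisher p is below 0.05 with RDV higher.

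| p | Points added, f = 0.25 | Points added, f = 1 | Equal windows | f = 0.25 | f = 1 |
|---|---|---|---|---|---|
| 20% | 0.22 | 0.86 | 1.84% | 2.10% | 3.05% |
| 30% | 0.30 | 1.21 | 1.96% | 2.29% | 3.57% |
| 40% | 0.37 | 1.47 | 1.90% | 2.28% | 3.79% |
| 50% | 0.42 | 1.66 | 2.01% | 2.46% | 4.27% |
| 60% | 0.44 | 1.75 | 1.90% | 2.37% | 4.33% |

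Per 200 participants, the added count runs from 0.4 to 3.5.

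**5. Sensitivity to visit timing**

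- Visits peaking at Day 28 (triangular over Days 23-33): the mean excess falls to 35/36 = 0.97 days, and the highest rejection rate at f = 1 falls from 4.3% to 3.5%.
- Every visit on Day 33 (outer bound): 3.1-6.0 points at f = 1 and 0.8-1.6 points at f = 0.25. At p = 40% and f = 1, rejection against RDV rises from 1.9% to 15.5%.

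**The case against.** The strongest reply is that Day 28 in 8.6.2 means the Day 28 visit. The protocol does use the term that way: 6.10 requires nothing after Day 28 although 6.5 lets the visit fall on Day 33, and those two sections fit together most easily if Day 28 is the visit. Section 8.6, the parent of 8.6.2, also sets one end for every group. On that reading the excess is zero. This stands as a possible reading. But 8.6.2 sets Day 28 beside a calculated date and takes the later of the two, which on its plain wording is a calendar rule, and the text does not settle the matter.

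A second reply is that the Part A SAP may already fix a common window. That cannot be checked here, so the point is about the protocol text, and the remedy is conditional.

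A third is that event rates, late hazard and visit timing are all assumed. That is correct, which is why ranges are shown.

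Two stronger readings are tempting, and the documents support neither:

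- **A gap of 7 or 12 days.** That is the difference on paper only. Section 8.6 keeps anything after the visit out of the summaries, and the visit cannot be later than Day 33.
- **Non-serious SOC events were not collected.** Before study medication starts, 7.3.1 says "the following types of events must be reported on the applicable eCRFs: all SAEs and AEs related to protocol-mandated procedures", and 7.3.2 continues "Following initiation of study medication, collect all AEs, regardless of cause or relationship, throughout the duration of the study". Section 7.1.1 also words the definition of an adverse event around receipt of an investigational product. Taken alone, these sections give SOC no start for full reporting. But the synopsis, 6.2.2, 6.3, 6.5 and Appendix 2 call for adverse event review with no arm named, 8.3.1.2 places undosed SOC participants in the Safety Analysis Set, and 8.5.2 needs an SOC proportion. Following the plan as a whole would collect these events, and nothing shows that any were missed. This is loose wording, not a demonstrated bias.

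**Conclusion.** The point holds as a minor one. On the calendar reading, the treatment-emergent window in 8.6.2 depends on dosing and can run past Day 28 only for RDV participants, while the proportion it defines is tested between RDV and SOC. The usable difference is at most 5 days (Days 29-33), and nothing for anyone whose visit is held by Day 28.

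Under 28-day risks of 20-60%, evenly spread visits and a late hazard of a quarter to all of the earlier one, it adds about 0.2-1.7 points and moves the chance of a false significant result against RDV from about 2% to 2.1-4.3% per comparison. The larger figures in the outer bound need every visit to fall on the last permitted day, which nothing in the documents suggests.

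The effect runs against RDV and leaves the primary endpoint alone. The case for acting is that the rule is easy to remove, not that it is likely to have changed a conclusion.

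**What to change.** For the Part A Fisher comparisons in 8.5.2, use one end date in all arms that does not depend on dosing. Keep last dose plus 30 days for descriptive RDV tables only. There are two options:

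- **Onset through calendar Day 28.** RDV events on Days 29-33 leave the test but stay in the descriptive tables. Participants seen on Days 23-27 are not fully observed to Day 28, but the rule is the same in every arm.
- **Onset through the Day 28 follow-up visit, as in 8.6.** No recorded event up to the visit is dropped. The length of observation then varies with the visit date in every arm.

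Part A has already been analysed (SAP 2.1.2 and 2.1.3). If the Part A SAP sets a common window, cite it in the clinical study report and do nothing more. If it does not, rerun this one comparison and report it there. The cost is a sentence of text and one table, with no new visits or data.

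As a wording note, reconcile 7.1.1, 7.3.1 and 7.3.2 with the sections that presuppose adverse event collection in SOC. This cannot alter Part A data.
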